1.2 Rationale and hypothesis

We propose a prospective, single-center, randomized trial to evaluate the impact of volume of injection for adductor canal block on patient recovery profile and block characteristics when performed for total knee arthroplasty.

2. Objectives

2.1 Primary outcome and endpoint

The primary purpose of this study is to compare the patient's ability to ambulate on POD 1 in patients that have received 5, 10 or 20 ml local anesthetic injection for SSACNB. This will be evaluated by determining how quickly a patient is able to ambulate over 10 meters on POD 1 (10 meter walk test).

2.2 Secondary outcomes and endpoints

The secondary purposes of this study are to compare the following perioperative variables:

Pre/Intraoperative Variables:

- Opioid consumption
- Sensory blockade
- Patient perceived discomfort with procedure
- Preoperative quadriceps strength
- Preoperative adductor strength
- SF12 mental component and physical component
- WOMAC and Knee Society Score
- UCLA activity score
- Preoperative range of motion
- Degree of varus/valgus deformity.

PACU Variables:

- Pain
- Opioid consumption
- Nausea
- Time in PACU (duration)
- Satisfaction with regional anesthesia
- Location of most severe pain

Floor Variables:

- Pain at rest
- Pain with activity
- Opioid consumption
- Nausea
- Duration of hospitalization

- Pain disturbing sleep
- Location of most severe pain
- Satisfaction with regional anesthesia

PT Variables:

- Pain with physical therapy
- Quadriceps strength
- Passive flexion/extension range of motion
- Postoperative quadriceps strength
- Postoperative adductor strength

3. Study design

This study is a prospective, single-center, randomized trial in which 60 subjects will be enrolled at the University of Wisconsin Hospitals and Clinics (UWHC). These subjects must meet study eligibility criteria and be scheduled to undergo an elective total knee arthroplasty. These subjects must also agree to undergo neuraxial anesthesia as the primary anesthetic for their surgical procedure and agree to an adductor canal block for postoperative analgesia. Patients will be randomized to receive 5, 10 or 20 mL of 0.5% bupivacaine injected into their adductor canal. Strength following the block and recovery characteristics following TKA will then be evaluated including pain, strength and ability to participate in physical therapy.

4. Study population

4.1 Inclusion criteria

Each patient must meet all of the following inclusion criteria to be enrolled in the study.

- 1) The subject is scheduled for elective unilateral TKA
- 2) The subject is ≥ 18 years and ≤ 80 years;
- 3) The subject's weight is between 70-120 kg; and
- 4) The subject's primary anesthesia care team has planned for a neuraxial anesthetic (i.e. spinal, epidural or combined-spinal epidural).
- 5) The patient agrees to receive an adductor canal block.
- 6) American Society of Anesthesiologists class 1-3

4.2 Exclusion criteria

Patients meeting any of the following exclusion criteria are not to be enrolled in the study.

- 1) Subject is < 18 years of age or >80 years of age;
- 2) Subject is non-English speaking;
- 3) Subject is known or believed to be pregnant;
- 4) Subject is a prisoner;
- 5) Subject has impaired decision-making capacity; per discretion of the Investigator
- 6) Symptomatic untreated gastroesophageal reflux or otherwise at risk for perioperative aspiration;
- 7) Any condition for which the primary anesthesia care team deems neuraxial anesthesia inappropriate;
- 8) Significant pre-existing neuropathy on the operative limb;

- 9) Significant renal, cardiac or hepatic disease per discretion of the investigator.
- 10) American Society of Anesthesiologists class 4-5
- 11) Known hypersensitivity and/or allergies to local anesthetics
- 12) Chronic Opioid Use (daily or almost daily use of opioids for > 3 months)

4.3 Protected populations

Prisoners

Due to the complexity of state and federal requirements governing the participation of prisoners in research, patients who are prisoners will not be considered for participation in this trial. In the unlikely event that a subject becomes a prisoner while participating in this trial, study procedures will stop and the subject will be returned to the clinical mode used prior to the intervention period or, if desired, a ventilator mode requested by the clinical care team.

Pregnancy

Patients who are known to be pregnant will be excluded from participation.

5. Trial interventions

The intervention portion of this study is the randomized assignment (1:1:1) to receive 5, 10 or 20 ml of 0.5% bupivacaine, incrementally injected. All studied volumes are well within the acceptable range for SSACNB. Randomization will be accomplished using an online service (www.randomizer.org) and prefilling sealed envelopes determining each subject's intervention group. In all other aspects, the subject will receive the standard of anesthesia care appropriate for their surgery or procedure as determined by the primary anesthesia team caring for the subject.

5.1 Allocation to intervention

Randomization of the volume of bupivacaine will be determined by opening a sequential, pre-sealed envelope with the group assignment designated within. Randomization will be accomplished using an online service (www.randomizer.org).

Each study subject and the anesthesia team caring for the patient in the operating room will be blinded to the study volume the patient received; however, the anesthesia provider performing the block (separate from the provider caring for the patient in the operating room) will not be blinded to the study volume injected and will have access to all monitors deemed appropriate by the primary anesthesia team caring for the subject. PACU/floor nursing and physical therapy staff will be blinded to volume of injection. The surgery team and study member responsible for pre/postoperative data collection will also be blinded to study drug volume.

6. Subject recruitment and consent

6.1 Subject identification and Screening

The study team will review the medical records of patients scheduled for an elective TKA to check for eligibility. Those who appear eligible will receive a phone call from a study team member who is also involved in their clinical care 1-7 days prior to their surgery. We will briefly describe the study procedures and voluntary nature, and answer any questions they have about it. If the subject is interested in participation, they will be instructed to arrive 1 hour earlier than their scheduled surgery arrival time so that there is time for consenting, considering participation, and confirming eligibility of those who agree to participate. Patients scheduled for an arrival time at or before 8:00 a.m. will not be eligible for the study. All protected health information used during the screening process of a potential subject will be the minimum necessary for the conduct of this study. Any protected information recorded will be destroyed at the end of the screening process.

6.2 Recruitment and consent

The identified patients will be given written information about the study at the time of check-in for their scheduled procedure. Once the anesthesia provider talks with the subject in order to confirm that they are a candidate for both spinal anesthesia and an adductor canal block (this conversation is standard care), a research team member will conduct the consent process in the surgery or procedure holding area. In order to ensure the candidate's privacy and confidentiality, the cubicle's curtain or room door will be closed. In a tone of voice insufficient for others to overhear the conversation and in the presence of only those immediately accompanying the patient and those who are directly involved with the patient's care, the study purpose, procedures, risks, benefits, and alternatives will then be discussed. The written information about the study provided to the candidate at the time of their check-in will be reviewed and they will be instructed to take as much time as needed to consider participation. While any study staff member may conduct the informed consent discussion and obtain informed consent, a study physician will be available at all times for any consent-related questions. Any questions that the candidate may have will be answered. Undue coercion will be prevented by stressing that the potential subject does not have to agree to participation and that the future care of the potential subject will not change regardless of the decision about participation. If the candidate has no further questions and would like to participate, they will be asked to sign the written informed consent document.

7. Activities and measurements

Prior to the procedure:

The subject will be met in the preoperative area by a staff anesthesiologist, who interviews and examines the subject. A full explanation of the neuraxial anesthetic and adductor canal block, including risks, benefits and alternatives, will be given and informed consent for anesthetic services obtained. Quadriceps motor strength and adductor strength will be assessed prior to any nerve blockade. Muscle strength will be assessed with the kio Sensor (Kio Inc., Madison, WI USA). The kio sensor is a force monitoring device that provides objective measurements of patient strength (traditional measurements or Manual Muscle Testing typically relies on subjective assessments by medical staff). To assess the subject's quadriceps and adductor strength, the kio sensor will be attached to the subject's ankle or upper leg and subject will be asked to forcefully extend the leg at the knee or adduct their leg. The kio Sensor is not currently commercially available and is currently in the development stage (see attached Phase I progress report – APPENDIX D). A sensory exam of the leg (temperature and pinprick) will also

be conducted prior to nerve blockade to determine baseline sensation of femoral, obturator and lateral femoral cutaneous nerves. For these tests, the jagged edges of a broken tongue depressor and alcohol swab will be used to produce pinprick and cold sensation. Subjects will be asked to report if sensation is normal, absent or decreased to both pinprick and cold.

From the subject's medical record the SF12 mental component and physical component, WOMAC and Knee Society Score, UCLA activity score, preoperative range of motion and degree of varus/valgus deformity will be collected. These scores and procedures are standard of care for all patients undergoing a TKA.

Adductor Canal Block Procedure:

An intravenous catheter will be placed, the subject will be transported to the block room or another room appropriate for provision of regional anesthesia and the subject will be pre-medicated with midazolam and/or fentanyl as needed at the discretion of the staff anesthesiologist.

Adductor canal blockade will be performed with the assistance of ultrasound guidance following sedation with midazolam and fentanyl as deemed appropriate by the staff anesthesiologist. The adductor canal will be located in a mid-thigh position. A Stimuplex needle (B. Braun Medical Inc., Melsungen, Germany) will be inserted in-plane to the ultrasound probe until the tip of the needle is appropriately positioned.

Study Randomization:

Following negative aspiration, SSACNB volume will be randomized and subjects will receive 5, 10 or 20 ml of 0.5% bupivacaine will be incrementally injected. Randomization of the volume of bupivacaine will be determined by opening a sequential, pre-sealed envelope with the group assignment designated within. All studied volumes are well within the acceptable range for SSACNB.

15 minutes post-block placement:

A sensory examination will be done 15 minutes following adductor canal block with pin prick (sharp end of tongue depressor broken in two) and alcohol swab in distribution of femoral, obturator and lateral femoral cutaneous nerve. Motor examination of quadriceps and adductor strength will also be tested 15 minutes following adductor canal blockade.

During the Surgical Procedure:

Neuraxial anesthesia will be performed as normally accomplished prior to initiation of the surgical procedure. Generally, this involves the administration of a combined-spinal-epidural anesthesia with 2.5 – 3 ml 0.5% bupivacaine administered into the intrathecal space.

In the operating room and procedural suite, monitors will be applied to the subject per established American Society of Anesthesiology (ASA) guidelines. At a minimum, these include non-invasive monitoring of blood pressure by automated cuff, oxygen saturation via pulse oximetry, heart rate and rhythm by 3-lead continuous electrocardiographic (ECG) tracing, core body temperature and expired carbon dioxide concentration. Additional monitoring may be applied on a case-by-case basis as deemed appropriate by the attending anesthesiologist. Ongoing sedation with midazolam, fentanyl and propofol will be provided as deemed appropriate by the staff anesthesiologist.

The surgical team will inject 50 ml 0.125% bupivacaine with 30 mg ketorolac (when deemed to be clinically appropriate) into the joint and posterior knee at the conclusion of the surgical procedure.

Post-Procedure:

The patient will be visited in the PACU to assess pain, opioid consumption, nausea, duration of PACU stay, satisfaction with regional anesthesia technique and location of most severe pain. This information will be ascertained by questioning the patient and reviewing the subject's medical record. Many of these assessments are routinely done as standard of care at the current time.

Postoperative analgesia will generally consist of scheduled toradol, scheduled Tylenol, MS Contin or Oxycontin, oxycodone PRN, and celebrex 100-200 mg BID or any combination of these. Therapy may be altered for patients with history of drug intolerances or allergies or any other contraindication to a specific therapeutic agent. Extended release opioid therapy may also be excluded in select elderly patients at the discretion of the orthopedic team. This therapy represents standard of care and is not altered by study involvement.

24 and 48-hours post-operative Follow-up:

The patient will be assessed on the floor for pain at rest, pain with activity, opioid consumption, nausea, pain disturbing sleep, location of most severe pain and satisfaction with regional anesthesia technique will be ascertained at 24 and 48 hours following the surgical procedure by questioning patient and review of medical record. Pain will be assessed using a Numerical Rating Scale (NRS) (0-10) where 0 represents no pain and 10 represents the worst pain imaginable. Duration of hospitalization will be obtained from review of medical record. Subjects with new or persistent complaints at 48 hours post-surgery that could be related to the study procedures will be offered continued follow-up by telephone or in-hospital room visit until the complaints resolve. Follow-up procedures would depend greatly on the clinical presentation but could include imaging, specialist consultation or surgical intervention. Subjects without complaints will be given appropriate information for contacting the research team if such complaints arise.

Physical therapy will determine pain with physical therapy, quadriceps strength, passive flexion/extension range of motion, postoperative quadriceps strength, postoperative adductor strength, and 10 meter walk test (gait velocity) at 24 and 48 hours postoperatively. All measurements of strength will be done using the Kiiro Sensor. Based on physical therapy team experience, patients are currently able to ambulate 10 meters in approximately 45 seconds on postoperative day one with 20 ml of local anesthetic injected into the adductor canal. The physical therapy team feels that ambulation velocity is generally limited by weakness and pain. However, we do not currently know if decreasing the dose of local anesthetic injected into the adductor canal will result in improved ambulation resulting from increased strength or worsened ambulation performance secondary to increased pain.

Concomitant Medications:

Analgesic and anti-emetic requirements for block placement, intraoperatively, in PACU, at 24 hours, 48 hours and during course of hospitalization will be extracted from the patient's electronic medical record.

7.1 Data entry

Information extracted from the subject's medical records includes date of service, subject name, date of birth, medical record number, age, gender, height, weight, data pertaining to the subject's pain, opioid consumption and ASA classification. In addition, SF12 mental component and physical component, WOMAC and Knee Society Score, UCLA activity score, preoperative range of motion and degree of varus/valgus deformity will be collected from the medical record.

All study data will be collected by a study team member on a standardized case report form (CRF) (see Appendix B) and transferred to an electronic Microsoft Excel spreadsheet suitable for export in coded format to a statistical analysis program. Data entry into electronic format will take place on a private computer away from potential viewing by non-study personnel. The paper and electronic data will be kept in the primary investigator's locked office in the Department of Anesthesiology. The computer will be pass-coded and linked to a secure Anesthesia Department server to allow access only to approved study personnel. At the end of seven years, all identifiable data will be destroyed as required by UWHC.

7.2 Subject withdrawals

At any point prior to or during the intervention period, the subject's clinical care team or a study physician may decide the subject should be withdrawn from the study. If a subject is withdrawn from the study for any reason the subject will then be followed according to the standard of care follow-up plan.

Study intervention will immediately stop and subject's clinical care team and a study physician will be immediately notified if one of the following occurs:

- 1) The subject suffers a severe adverse perioperative outcome that precludes participation in physical therapy or measurements of motor strength or sensory examination

In the event the study method is terminated, the reason for termination will be documented on a case report form.

8. Data analysis and statistical considerations

All data will be summarized using standard descriptive statistics, including mean, standard deviation, minimum, maximum, median, inter-quartile range, and confidence intervals, as appropriate. The data will be presented graphically (where possible) using scatter plots, profile plots, or histograms. Data analyses will be performed on an intent-to-treat basis using SAS (SAS Institute Inc., Cary, NC; version 8.2 or greater) or Minitab (Quality Plaza, State College, PA; version 13.0 or greater). The primary analyses will consist of comparing the three study volumes of injection for superiority. For all tests, statistical significance will be defined as a p-value less than 0.05. ANOVA and two-sample t-test will be used to compare the data between the three groups or between any two individual groups. Repeated measures ANOVA will be used to analyze multiple follow-up data points. Patients with missing longitudinal data will be handled by either using data imputation methods to replace the missing data or via the use of repeated measures ANOVA to better approximate the average values at each time point. Bonferroni correction will be utilized to counteract the problem of [multiple comparisons](#) and control the [familywise error rate](#).

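### Optional gain for secondary outcomes: the preoperative strength and range-of-motion values already collected could be used as covariates, and section 8 names none

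*Combined protocol and SAP*

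**What the plan says.** The analysis methods are all in section 8. For group comparisons, "ANOVA and two-sample t-test will be used to compare the data between the three groups or between any two individual groups". For longitudinal outcomes, "Repeated measures ANOVA will be used to analyze multiple follow-up data points". Missing longitudinal values are to be handled by imputation or "via the use of repeated measures ANOVA to better approximate the average values at each time point". None of these sentences names a covariate, and no analysis of covariance appears elsewhere in the document.

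Section 7 and the schedule of activities show what is collected:

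- **Before the block:** "Quadriceps motor strength and adductor strength will be assessed prior to any nerve blockade".
- **Randomisation:** this comes later, with the needle in place: "Following negative aspiration, SSACNB volume will be randomized".
- **15 minutes after the block:** "Motor examination of quadriceps and adductor strength will also be tested 15 minutes following adductor canal blockade".
- **After surgery:** physical therapy records "passive flexion/extension range of motion, postoperative quadriceps strength, postoperative adductor strength, and 10 meter walk test (gait velocity) at 24 and 48 hours postoperatively". Section 7 requires the same sensor for every strength measurement.
- **Range of motion before surgery:** sections 7 and 7.1 take it from the medical record and do not say whether it is active or passive.

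No preoperative 10 meter walk test is scheduled.

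**The concern.** Motor strength is central to the trial's reasoning. The introduction asks whether a larger volume weakens the quadriceps, and section 7 says it is unknown whether a smaller volume would help ambulation through strength or hinder it through pain. Patients are likely to differ in strength before any block. If those differences carry over to the postoperative readings, an unadjusted analysis leaves them in the error term although the value that could remove them is already on the case report form.

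What is at stake is interval width for strength and, less surely, for range of motion. Section 8.1 describes the trial as preliminary and hypothesis-generating. With 20 per arm and a Bonferroni correction, the width of these intervals determines how much the strength results can tell a later trial.

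**Working it through.** **Inputs from the documents.** Three arms, 1:1:1 (section 5). 20 enrolled per arm and 16 required before the dropout allowance (section 8.1). Significance level 0.05 with Bonferroni correction (section 8).

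**Assumptions.** Tests are two-sided. Bonferroni covers three pairwise comparisons, since the plan does not give the number. The outcome SD is set to 1. The correlation ρ between the preoperative value and the outcome is not in the documents, so a range of 0 to 0.7 is shown.

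**The plan's own figure.** Section 8.1 assumes a 15-second difference and an SD of similar size, a ratio of 1. The two-sided normal approximation gives n = 2 × (1.960 + 0.842)² / 1² = 15.70, so 16 per group. The stated sample size reproduces. It concerns the walk test and is not in question here.

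**Is the pre-block value a proper baseline?** Strength is tested before any block, and the volume is assigned only after negative aspiration. The assigned volume therefore cannot affect the pre-block value. The 15-minute value follows the injection and can be affected, so it is an outcome and not a possible covariate.

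**Unadjusted half-width of a pairwise difference at one time point**, three-arm pooled variance: t(3n−3) × √(2/n).

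- n = 20: 2.0025 × 0.3162 = 0.633 SD
- n = 16: 2.0141 × 0.3536 = 0.712 SD

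**Adjusted half-width:** t(3n−4) × √[(2/n) × (1−ρ²) × (1 + 1/(3n−5))]. The last factor is the expected cost of estimating the slope: 1 + 1/55 = 1.0182 at n = 20, and 1 + 1/43 = 1.0233 at n = 16. For example, at n = 20 and ρ = 0.5: 2.0032 × √(0.1 × 0.75 × 1.0182) = 0.554 SD.

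| Assumed ρ | n = 20, 95% | Change from 0.633 | n = 16, 95% |
|---|---|---|---|
| 0 | 0.639 | about 1% wider | 0.721 |
| 0.3 | 0.610 | about 4% narrower | 0.688 |
| 0.5 | 0.554 | about 13% narrower | 0.624 |
| 0.7 | 0.456 | about 28% narrower | 0.515 |

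**With Bonferroni (0.05/3) at n = 20.** Unadjusted: 2.4667 × 0.3162 = 0.780 SD. Adjusted, with t(56) = 2.468: 0.751, 0.682 or 0.562 SD at ρ = 0.3, 0.5 or 0.7. The proportional gains are the same.

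**Break-even.** Adjustment lowers the variance when (1−ρ²) × (1 + 1/(3n−5)) is below 1, that is, when ρ exceeds √(1 − 1/1.0182) = 0.13 at n = 20, or √(1 − 1/1.0233) = 0.15 at n = 16.

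**Simulation check** (3 × 20 patients, 3,000 runs per ρ): adjusted half-widths of 0.638, 0.609, 0.555 and 0.456 SD at ρ = 0, 0.3, 0.5 and 0.7, against 0.632 to 0.634 SD unadjusted.

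**The case against.** The strongest reply is that this is a preference for efficiency and not an error. That stands. Randomisation makes the unadjusted comparison valid, no sample size or decision rests on these outcomes, and at ρ = 0.3 the gain is only about 4%. There are also reasons to expect a modest ρ. Postoperative strength is measured 24 to 48 hours after major knee surgery. The 15-minute test may follow sedation given for the block. The chart range of motion may not have been measured in the same way as the passive range recorded by physical therapy. These points limit the size of the gain. They do not bias a covariate analysis, and the loss if ρ is zero is about 1%.

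A second reply is that the plan names two-sample t-tests, so the pooled figure is not exactly what it would report. That is correct but small: on two arms alone, t(38) × √(2/20) = 2.0244 × 0.3162 = 0.640 SD, against 0.633 SD.

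Some stronger readings may occur to a reader, and the documents do not support them:

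- **The strength results would be biased without adjustment.** They would not be, because allocation is randomised.
- **The primary analysis is affected.** The walk test has no preoperative value, so it has no like-for-like baseline to use.
- **Strength before and after surgery is not comparable because the sensor site is left open** ("ankle or upper leg and subject will be asked to forcefully extend the leg at the knee or adduct their leg"). The sentence reads naturally as one site for each of the two tests, and section 7 requires the same sensor throughout.
- **The plan uses change scores, or tests baseline balance.** No change score is proposed. Section 2.2 lists preoperative items among the variables to compare, but no section specifically prescribes tests of them.

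**Conclusion.** The point holds as an optional improvement in precision, confined to quadriceps strength, adductor strength and range of motion. The plan is valid as written. Adjustment could narrow the strength intervals by about 4% to 28% if ρ lies between 0.3 and 0.7, and would widen them by about 1% if ρ is zero. A reader might infer that it is certain to sharpen the comparisons, but the documents give no correlation, so neither a gain nor its size is assured. The case is better for strength, which is measured with one sensor throughout, than for range of motion, whose preoperative mode of measurement is not stated. The figures assume two-sided tests, a common outcome variance across arms, a linear relation with baseline, and three pairwise comparisons wherever Bonferroni is applied.

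**What to change.** In section 8:

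1. For strength at 24 and 48 hours, keep the repeated measures model and add the pre-block value of the same muscle group as a covariate, with a baseline-by-time term.
2. For strength at 15 minutes, use an ANCOVA on the pre-block value.
3. Never use the 15-minute value as a covariate.
4. For passive range of motion at 24 and 48 hours, use the same model with the chart value, and note that the gain may be smaller.
5. Take the pairwise contrasts from these models, with the Bonferroni correction already planned.
6. Replace a missing preoperative value by the mean over all arms, without using arm or outcome, so that no patient is lost from the model.
7. Leave the walk-test analysis without this covariate.

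The choice should be written down before the outcome data are seen, so that adjusted and unadjusted results cannot be chosen between afterwards. The cost is a few sentences in section 8, one degree of freedom for the slope at each time point, and an interval about 1% wider if baseline and outcome are unrelated. No new data are needed.

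### Section 8 names only tests of means, but location of most severe pain is a nominal outcome with no mean, so the named test gives a result that depends on how the sites are numbered

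*Combined protocol and SAP*

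**What the plan says.** The whole testing rule is in Section 8 (Data analysis and statistical considerations). For between-group comparisons it says "ANOVA and two-sample t-test will be used to compare the data between the three groups", and extends this to any pair of groups. For longitudinal data it says "Repeated measures ANOVA will be used to analyze multiple follow-up data points". The rule is not limited by type of outcome. No chi-square, exact, rank-based, ordinal or log-scale method appears in the documents, and nothing says what to do if the assumptions of ANOVA fail.

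Median and inter-quartile range do appear, but only for description: "All data will be summarized using standard descriptive statistics, including mean, standard deviation, minimum, maximum, median, inter-quartile range, and confidence intervals, as appropriate". That closing qualifier belongs to the summaries, not to the tests.

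The secondary outcomes to be compared are in Section 2.2. They include "Location of most severe pain", listed under both the PACU and the floor variables. Section 7 has it asked in the PACU and again at 24 and 48 hours. The list also includes opioid consumption, time in PACU and "Duration of hospitalization". Sensory blockade is graded in three levels; Section 7 states that "Subjects will be asked to report if sensation is normal, absent or decreased to both pinprick and cold".

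**The concern.** A pain site is a label. It has no mean and no variance, so ANOVA, the t-test and repeated measures ANOVA can be run on it only after each site is given a number. The test then compares the averages of those numbers. Another numbering of the same answers gives another p-value, and the plan offers no reason to prefer one numbering.

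The outcome matters to the trial's question. Section 7 says it is unknown whether a smaller volume helps walking by sparing strength or harms it by leaving more pain, and where the pain is felt bears on that. Section 8.1 says the data will be used to generate hypotheses for later trials. An analyst who quietly uses a categorical test instead departs from the written plan and chooses the test after seeing the data.

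A second, conditional issue concerns opioid consumption, PACU time and length of stay. These cannot fall below zero and may be right-skewed, in which case a comparison of raw means can lose power.

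**Working it through.** **The plan's own figure.** Section 8.1 assumes a difference of 15 s and an SD of about 15 s, with significance level 0.05 and power 0.80. For two means, n per group = 2 × (1.960 + 0.842)² × (15/15)² = 15.7, rounded up to 16. This matches the stated 16. It concerns walk time and does not depend on anything below.

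**Nominal outcome.** The documents give no data on pain location, so both tables below are assumed. The plan supplies only the 20 per arm (Section 8.1).

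Table A has four sites, with counts by arm of 10/4/4/2, 6/8/3/3 and 3/13/2/2. There are 24 ways to number four sites 1 to 4. One-way ANOVA under each gives these extremes:

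- Sites numbered 1, 4, 2, 3: arm means 2.00, 2.65 and 3.25; between-arm sum of squares 15.63, within-arm 86.30. F = (15.63/2) / (86.30/57) = 5.16, p = 0.009.
- Sites numbered 4, 3, 1, 2: arm means 3.00, 2.85 and 2.85; between-arm sum of squares 0.30, within-arm 61.10. F = (0.30/2) / (61.10/57) = 0.14, p = 0.87.

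Chi-square does not use the numbering. The site totals are 19, 25, 9 and 7, so the expected counts per arm are 6.33, 8.33, 3.00 and 2.33. The statistic is 9.73 on 6 degrees of freedom, p = 0.14. Six of the 12 expected counts are below 5, so even this p-value is approximate and an exact test is the safer choice at this sample size.

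Table B, with counts 10/4/4/2, 6/6/4/4 and 4/4/10/2, behaves the same way: ANOVA p from 0.06 to 0.63, chi-square p = 0.21. The width of the range depends on the table. The dependence on numbering does not.

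**Possibly skewed outcomes.** No distribution is given for opioid consumption, PACU time or length of stay, so the range has to be shown. The assumptions are a lognormal outcome, a two-fold difference between two arms, 20 per arm and two-sided 0.05. Simulated power:

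| Log-SD | t-test on raw values | Wilcoxon |
|---|---|---|
| 0.5 | 0.98 | 0.99 |
| 0.7 | 0.77 | 0.84 |
| 1.0 | 0.40 | 0.54 |

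These figures carry simulation error of up to about 0.01. In three-arm lognormal simulations at 20 per arm with log-SD from 0.5 to 1.2, the type I error of ANOVA stayed at or below about 0.045.

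**Three-level ordinal outcome.** Level probabilities of 0.6/0.3/0.1 in two arms and 0.2/0.4/0.4 in the third, 20 per arm, levels scored with equal spacing: ANOVA power 0.87, Kruskal-Wallis 0.87.

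**The case against.** The best defence is that Section 8 speaks of comparing the data without saying that every listed variable is meant. Its neighbouring sentences concern means, medians and the primary analyses, so the tests may be intended for quantitative outcomes, with categorical items simply left out. No competent analyst would average site codes. This softens the point but does not remove it: on that reading the plan has no test at all for a listed outcome, and the same lines are needed.

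The objection is right about several stronger readings that a reader might infer:

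- *That ANOVA performs poorly for sensation or other ordered ratings.* No power loss was found for a three-level outcome. What remains is the assumption of equal spacing between levels, which is a matter of preference.
- *That the t-test is clearly inadequate for opioid use and durations.* This rests on assumed skew. At log-SD 0.5 the loss is about one point. A difference in mean dose or mean stay is also a legitimate target, which a rank test does not estimate.
- *That false positives are inflated.* The skewed-data simulations show no inflation for ANOVA.
- *That the p-value for pain location can be moved almost anywhere.* The 24 numberings of Table A give only 12 distinct p-values, because reversing a numbering changes nothing, and Table B spans a narrower range.

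**Conclusion.** The point holds for location of most severe pain: the only tests named do not suit a nominal outcome, and their result depends on an arbitrary choice of codes. This follows from the type of outcome. Only the size shown (0.009 to 0.87 against 0.14) rests on an assumed table with four sites.

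For opioid consumption, PACU time and length of stay the point is conditional. The loss against Wilcoxon runs from about 1 to 14 percentage points over log-SDs of 0.5 to 1.0, for an assumed lognormal outcome with a two-fold difference. For the sensation grades no harm was shown.

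All the affected outcomes are secondary, Section 8.1 calls the study preliminary, and the 10 meter walk test and its 16 per group are untouched. The point is minor to moderate. It should not be read as a threat to the trial's main result.

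**What to change.** In Section 8:

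1. Limit ANOVA, t-tests and repeated measures ANOVA to quantitative outcomes.
2. Compare location of most severe pain, and any items recorded as yes/no, by the Fisher-Freeman-Halton exact test, or by chi-square where expected counts allow. Do this separately in the PACU, at 24 hours and at 48 hours.
3. For opioid consumption, PACU time and duration of hospitalization, pre-specify a log-scale or rank-based analysis (Kruskal-Wallis with pairwise Wilcoxon) to be used if the data are clearly right-skewed. State in advance how that will be judged, preferably on the pooled data without regard to arm. Where zeros occur, use the rank-based form.
4. Optional: a rank test or proportional-odds model for the sensation grades.

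The cost is a few lines of text, with no added patients, visits or measurements. The small downside is that effects on these outcomes will not be reported as differences in means; group medians, already among the planned summaries, can be shown beside the tests.
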